6. Check one of the boxes below based on your study design and provide the references from the protocol for the information in the table:

Prospective Study  Retrospective Study  Both

**NOTE:** If retrospective is checked, some of the below categories may not apply and can be marked as "Not applicable."

Safety Issues	Reference the protocol page and section.	If not referenced in the protocol, cite document type, page and section where it is referenced.
What Safety Information is Collected	N/A	

How will Safety Information be collected	N/A	
Frequency of Safety Data Collection	N/A	
Safety Conditions that Trigger Immediate Suspension of Research	N/A	
Procedures to notify participants or PCP of findings affecting participants' health or welfare	Section 16, 10.1; 11.1; 13.3	
Procedures to minimize risk	Section 16	
Inclusion Criteria	Section 16, 7.1	
Exclusion Criteria	Section 16, 17.1	

7. Will an independent Data Safety Monitoring Board (DSMB) or a Data Monitoring Committee (DMC) monitor the project? Yes  No

7.1. If yes, provide a description of responsibilities to include frequency of meetings:

7.2. If no, provide the protocol section and/or page where the data safety and monitoring plan is described, to include statistical tests to be used for analyzing the safety data to determine if harm is occurring.

*The PI will be responsible for monitoring the study. All participants will be given anticipatory guidance on when to seek medical attention. In addition, participants will be asked to report to the study team any events they feel resulted from participation in the study. They can either present in person or call on the study team. Study staff will contact the participant to collect any information on the issue and then the PI will review and determine whether it is okay to proceed, further investigation is needed, or the participant should stop the study. The PI will review all report of adverse events within 24 hours of their occurrence and on a monthly basis determine if a change in protocol is indicated due to the occurrence of adverse events.*

8. If the PI is not a clinician, is there an appropriately credentialed and privileged clinician who has been designated as a member of the study team to make required decisions to help protect the health of the subject, review data on adverse events, and report new findings? Yes  No  N/A

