#### 4. Study Procedures

##### 4.1. Study Design

4.1.1. Describe experimental design of the study. Include sequential and/or parallel phases of the study, including durations, and explain which interventions are standard of care.

*The study design is a 9-month, randomized, 2-arm, parallel, open-label feasibility trial. Eligible participants will be randomized to a brief single Motivational Interviewing (MI) session and SUMMIT versus a pain monitoring app. All participants will also be provided a referral to speak with a clinical pharmacy specialist about their medications and options for tapering. Feasibility and outcomes planned for a full-scale RCT will be collected at one-, three-, six-, and nine-months post-randomization. Opioid dose and adverse events (AEs) will be collected bi-weekly. We will send the link to the questionnaire to the participant if they have given permission to contact via email, otherwise we will send them the link via text, or read it aloud to them. Given the urgency to develop effective programs to support tapering efforts, we will perform interim analyses at three months. If positive, results of these analyses would expedite onset of the planned full-scale RCT.*

*Eligible patients on long term opioid treatment (LTOT) or on buprenorphine will be identified through VA Corporate Data Warehouse (CDW). Receipt of opioid medication will be defined as any dispense of a VA formulary category CN101 drug. Veterans having liquid methadone dispensed in the previous six months will be excluded. Because all methadone for the treatment of OUD is dispensed at federally licensed opioid treatment programs, we will cross check all methadone dispenses with stop code 523, the code used exclusively in those programs. For Veterans who remain eligible, a focused electronic medical record (EMR) review will be conducted to determine whether the Veteran is currently receiving liquid methadone or participating in a concurrent pain or opioid-related research study, and to check for evidence of hearing or visual impairments (not corrected with hearing aids or glasses), cognitive impairment or psychiatric condition. A list of eligible Veterans will be compiled into an Excel file and saved on the secured CHERP server. This list of potential subjects will NOT be printed out.*

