Quantitative statistics will be performed by SAS, version 9.4. and will be performed by [name] (PI) and [name] (co-I). As we are proposing a feasibility trial, most of the analyses are descriptive. We will use descriptive characteristics to describe the study population, all feasibility outcomes, and the distribution of the primary and secondary outcomes planned for the full-scale trial. We will ascertain the distributional characteristics, response rates as well as the percent of the missing data for all baseline and follow-up measures at each time point. Although not powered to detect significant between-group, we will compare differences in the primary and secondary outcomes to examine preliminary trends that may inform the design of the full-scale trial. We will use regression analyses to examine the association between group assignment and the primary and secondary outcomes. Group assignment and time will be modeled as fixed factors and participants as random factors. Separate models will be conducted for each outcome. We will perform an interim analysis at three months to evaluate trends in the recruitment rate, use of SUMMIT, and opioid dose reduction. These results may support earlier initiation of the planned full-scale RCT. Exploratory mediation analyses will be used to examine the processes underlying change. We will use the product of coefficients method to determine whether 1) "dose" (amount of use with specific SUMMIT components) and 2) change in specified theoretical constructs mediate the relationship between treatment assignment

and clinical outcome measures. (86) We will also examine the effect of compliance on change in theoretical constructs and the primary and secondary outcome measures using a Complier Average Causal Effect analysis. (87) To examine heterogeneity, exploratory moderating analyses will be performed by including an interaction term (moderator X intervention status) in a multiple linear regression model. We will construct separate models for the following five possible moderators: age, baseline opioid dose, duration of LTOT, prevalent comorbid mental illness, and baseline intrinsic motivation. Although we will not be sufficiently powered to perform definitive mediation or moderating analyses, the data generated from this feasibility study will determine which measures to include in the full-scale trial.

10. **Withdrawal of Subjects**

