10.1. **Describe any anticipated circumstances under which subjects will be withdrawn from the research without their consent.**

Subjects diagnosed with opioid use disorder (OUD) or substance use disorder (SUD) during the study will be withdrawn and referred for treatment. The study team will notify their PCP if this is the case. Subjects exhibiting inappropriate behavior online or with a peer specialist may also be withdrawn.

10.2. **Describe the consequences of a subject's decision to withdraw from the research and the procedures for orderly termination of participation by the subject (e.g., the subject contacting the investigator for an end-of-study visit).**

No consequences for withdrawal. Once we are notified of a participant's decision to withdraw, we can continue to use information about them that has been collected up to that point. No information will be collected after a participant formally withdraws.

11. **Reporting**

11.1. **Include procedures for reporting unanticipated problems, serious adverse events, and protocol deviations.**

Protocol deviations, unanticipated/unexpected problems will be reported to the IRB within 5 business days of discovery. We will use the CMCVAMC serious-adverse event form for reporting SAEs, UADEs, and any other unanticipated/unexpected problems. We will also use the CMCVAMC Protocol Deviation form for reporting any protocol deviations. Any adverse event would be reported to the IRB at continuing review. Further, if the patient develops any concerns with their medication treatment plans, particularly effects related to their opioid tapers, these will be referred to their PCP.

12. **Privacy and Confidentiality**

12.1. **Describe whether the study will use or disclose subjects' Protected Health Information (PHI).**

For Veterans, we will need to obtain name, date of birth, complete mailing address, race, gender, and medical history. This information will be used only in our analysis and to contact the Veteran (mailing address); no information will be disclosed to others outside our study team. The applications being used by the study, likewise, will not use or disclose the participants PHI.

12.2. **Describe the steps that will be taken to secure the data (e.g., training, authorization of access, password protection, encryption, physical controls, Certificates of Confidentiality, and separation of identifiers and data)**

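### Item 10.1 withdraws participants diagnosed with OUD or SUD from the research, and nothing provides for dose and adverse event follow-up afterwards

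*Combined protocol and SAP*

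**What the plan says.** Section 16, item 10.1 lists who is withdrawn from the research without their consent. Its main entry is: "Subjects diagnosed with opioid use disorder (OUD) or substance use disorder (SUD) during the study will be withdrawn and referred for treatment". The primary care provider is told. The item does not mention data after the withdrawal.

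Item 10.2 deals with a participant's own decision to leave. It keeps earlier data ("we can continue to use information about them that has been collected up to that point") and then says: "No information will be collected after a participant formally withdraws".

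The data at issue are set out in item 4.1.1: "Opioid dose and adverse events (AEs) will be collected bi-weekly". Fuller assessments follow at one, three, six and nine months.

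On reporting, item 9.2 promises "response rates as well as the percent of the missing data for all baseline and follow-up measures at each time point", without naming arm or cause. Its between-group comparisons cover the primary and secondary outcomes. AEs, diagnoses and withdrawals are not named. It also says: "We will perform an interim analysis at three months to evaluate trends in the recruitment rate, use of SUMMIT, and opioid dose reduction".

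Section 4, question 7.2 asks for the "statistical tests to be used for analyzing the safety data to determine if harm is occurring". The answer describes review of individual cases: "The PI will review all report of adverse events within 24 hours of their occurrence", plus a monthly PI decision on whether the protocol should change. No tabulation is described.

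**The concern.** A new diagnosis of OUD or SUD arises after randomisation, and in a tapering trial it may itself be a harm. The weeks after it are when AEs and dose changes are of most interest for a program meant to make tapering safe. If the reports stop there, the loss of data is tied to the outcome rather than to ordinary attrition.

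The arms need not be affected equally. Only the SUMMIT arm has a motivational interviewing session and optional contact with a peer specialist, which may give more occasions for a problem to surface. That is an inference; the documents do not say it. If diagnoses did differ by arm, the arm with more of them would have more of its later AEs and doses uncollected, and no planned table names the split by arm or cause. The results are meant to inform a full-scale trial, and the three-month look may bring its start forward.

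**Working it through.** **Inputs from the protocol (Section 16).** 64 participants randomised 1:1, so 32 per arm (items 4.1.1 and 9.1). Up to 18 bi-weekly reports over nine months (item 5.4). Assessments at one, three, six and nine months (item 4.1.1). The documents give no rate of OUD or SUD diagnosis and no AE rate.

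**The plan's own figure.** The drop-out allowance in item 9.1 reproduces: 48 / (1 − 0.25) = 64. That leaves room for 16 losses. It covers how many are lost, not whether the loss is related to outcome.

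**Reports lost per participant, if 10.2 is applied to 10.1.** 18 reports / 9 months = 2 per month, so a diagnosis at month m loses 18 − 2m.

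| Diagnosis at | Reports made | Reports lost | Assessments lost |
|---|---|---|---|
| 1 month | 2 | 16 of 18 | three, six, nine months |
| 3 months | 6 | 12 of 18 | six, nine months |
| 6 months | 12 | 6 of 18 | nine months |

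For the three-month dose look, 6 reports are due by then. A diagnosis at one month loses 6 − 2 = 4 of them.

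**How many participants (rates assumed).** At a diagnosis rate of 3%, 32 × 0.03 = 1.0 per arm is expected, and the chance of at least one in an arm is 1 − 0.97^32 = 62%. At 20%, 32 × 0.20 = 6.4 are expected and the chance is above 99%.

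**What it could do to AE comparisons (every rate assumed).** Take d diagnoses in an arm, all at three months; 0.10 AEs per fortnight in everyone before diagnosis and in those never diagnosed; and a rate r after diagnosis.

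- Full follow-up: (32 − d) × 18 × 0.10 + d × (6 × 0.10 + 12 × r)
- Reports stopped: (32 − d) × 18 × 0.10 + d × 6 × 0.10

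With d = 4 in SUMMIT, d = 1 in control and r = 0.30:

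- Full: SUMMIT 50.4 + 4 × 4.2 = 67.2; control 55.8 + 4.2 = 60.0; difference +7.2.
- Stopped: SUMMIT 50.4 + 2.4 = 52.8 over 528 fortnights; control 55.8 + 0.6 = 56.4 over 564; difference −3.6.
- Reports lost: 4 × 12 = 48 of 576 (8.3%) v 12 of 576 (2.1%).
- Rate excess: 7.2 / 576 = 1.25 per 100 fortnights in full; 52.8/528 − 56.4/564 = 0 when stopped.

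| Rate r after diagnosis | Full, SUMMIT v control | Stopped | Rate excess lost per 100 fortnights |
|---|---|---|---|
| 0.30 | 67.2 v 60.0 | 52.8 v 56.4 | 1.25 |
| 0.20 | 62.4 v 58.8 | 52.8 v 56.4 | 0.63 |
| 0.10 (no rise) | 57.6 v 57.6 | 52.8 v 56.4 | 0 |

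With equal diagnoses and equal event rates the between-arm bias is zero. The recorded rate excess of 0 in every row follows from setting the pre-diagnosis rates equal. The table shows what the bias depends on; it does not estimate it.

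**Precision.** 4/32 v 1/32 is 12.5% − 3.1% = 9.4 points, Newcombe 95% CI −5 to +25. By-arm tables would be descriptive only.

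**The case against.** The strongest objection is textual. Both the prompt and the answer in 10.2 concern a participant's own choice, and 10.1 is silent on data. The consent form is not in the published document, so what participants were told cannot be checked. This stands to the extent that the stop is inferred, not stated. But 10.1 withdraws people from the research, the closing sentence of 10.2 is general, and no section supplies follow-up. If follow-up is intended, the protocol needs to say so.

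Second, a reader might infer that the rule makes SUMMIT look safer than it is. The documents do not support that. The 4 v 1 split, the AE rate and its rise are all invented for illustration, and the bias vanishes under equally plausible inputs.

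Third, a reader might infer that these participants drop out of the analysis, or that the dose models are biased. Earlier data are retained, so follow-up is truncated rather than absent. Item 9.2 models participants as random factors, which uses partial follow-up and tolerates drop-out that depends on doses already observed. Any remaining effect is not quantified here.

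Fourth, harm is not invisible. Reported events go to the PI within 24 hours and to the IRB, the primary care provider hears of the diagnosis, and item 9.2 gives overall response rates. That is fair. What these do not show is an imbalance between arms, or events that go unreported after withdrawal.

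Finally, this is a small, mainly descriptive feasibility trial, and ending dose collection once OUD treatment begins is a coherent choice for interpreting dose. It is less defensible for AEs.

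**Conclusion.** The point holds as a gap in follow-up that is cheap to close. Withdrawal under 10.1 is triggered by a post-randomisation event that may be a harm; no section provides for later data; and on the natural reading of 10.2 the dose and AE reports end there. The firm part of the size is the loss per participant: 16, 12 or 6 of 18 reports for a diagnosis at one, three or six months. That rests on applying 10.2 to 10.1 and on evenly spaced reports.

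The documents cannot establish that the between-arm AE or dose comparison is biased, in which direction, or by how much. The absence of a by-arm table would, taken alone, be missing detail. It matters here because the table would show whether the truncation was uneven. None of this disputes the sample size.

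**What to change.** 1. In item 10.1, have participants diagnosed with OUD or SUD stop the study intervention and be referred, but with their agreement continue the bi-weekly dose and AE reports, and review of the CDW and CPRS sources already named in Section 11, question 2, to nine months. In item 10.2, state that the stop on data collection applies only to a participant's own decision to withdraw.
2. As part of that change, state how opioid dose is recorded after a move to OUD treatment, so that the switch is not counted as a taper. This matters mainly once follow-up continues.
3. In item 9.2, report descriptively by randomised arm the number and percentage with at least one AE, at least one SAE, and an OUD or SUD diagnosis; withdrawals by cause and time; and the number of bi-weekly reports returned.

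The cost is revised wording in 10.1, 10.2, 9.2 and the consent text, an IRB amendment, and a little extra follow-up and chart review for a few people. It needs no new instrument and no more participants. Some will decline, so the loss is reduced rather than removed.

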***1 Investigator, 1 co-investigator, 2 Collaborators (as listed in current staff form)***

6. **Will specially obtained software be used? Yes  - See below No**

6.1. **If yes, describe the software, the source of the software, whether a license will be required and who will fund the license, as well as any data that will be stored in temporary files on the computer's hard drive.**

7. **Will any web-based applications be used? Yes  - See below No**

7.1. **If yes, identify the application and its security features. Indicate how it will be used, e.g., for recruiting subjects, completing questionnaires, or processing data.**

***The Manage My Pain app will be used for participants randomized to the control intervention. This app is freely available on both Android and iPhone operating systems.***

***SUMMIT will be used for participants randomized to the experimental intervention. Both of these web-based applications will be used on their personal mobile phones that will not collect identifiable data but solely used as educational web-tools for the participants.***

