#### ***Randomization groups:***

*Experimental Intervention: Participants randomized to the experimental intervention will participate in a Motivational Interviewing (MI) session lasting between 30 and 60 minutes with a study coordinator. All MI sessions will be audiotaped using a VA-approved digital recorder and transcribed verbatim. Participants will subsequently be shown how to access SUMMIT through a web link via a set of unique anonymized login credentials and to navigate the components of SUMMIT on one or more devices, depending on their preference. They will then be trained on how to complete the outcome surveys **on RedCap, which will be sent via email**.*

*The SUMMIT application includes multiple modules for participants to learn about opioid tapering as well as other ways to manage their pain. As part of the application, participants will also have the option to connect with a peer support specialist at the VA who has previous experience with chronic pain and opioid tapering.*

**Control Intervention:** Participants randomized to the control intervention will use an eHealth comparator: Manage My Pain(iPhone, Android). This app includes a pain monitoring functioning only, and thus will only minimally overlap, if at all, with SUMMIT's components. Control participants will not participate in a MI session. Participants will download the app and be shown how to use the Manage My Pain app and trained how to complete the outcome surveys

In order to help participants set up their mobile applications, the study coordinator will set up a video appointment through the VA's virtual care manager (VCM) and using the VA video connect (VVC) software. The appointment is coordinated using the participants email address, and through the video appointment the coordinator will help the participant set up their device.

**4.1.2. Include a description of how anticipated risk will be minimized and include an analysis of risk vs. potential benefit.**

*Veterans with anxiety or concerns will be referred to their primary care physician. Each Veteran will be assigned an ID number that is not related to any PHI. The key containing the link between the study ID number and participant will be maintained on the CMCVAMC's secure server*

*(\\vhaphifpccherp.v04.med.va.gov\shares2\[name]) on a separate folder from the collected data. Only [name] (PI) and study staff will have access to this key.*

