*Neither the SUMMIT app nor the Manage My Pain app will be collecting any personal health information. The SUMMIT app will collect aggregated data on usage of features of the app. The Manage My Pain app once downloaded requires the user to complete an end user agreement that specifies how any collected data will be used and shared. The app does aggregate non-personal information from all users, including pain records, age, geographic location, and gender, which is stripped of personal information. There is an option to sign up for an online account through the Manage My Pain app, which would collect additional information, however study participants will be advised not to do so.*

**4.1.3. Provide description of the study population (delineate all categories of subjects – patients, providers, family members, employees, etc.). Include anticipated enrollment numbers.**

*This projects involves the recruitment of 64 Veterans. Patient recruitment at the CMCVAMC will target male and female patients enrolled in long term opioid treatment (LTOT).*

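### The peer-specialist ground for involuntary withdrawal in Section 16, 10.1 can arise only in the SUMMIT arm, and it takes the participant out of the research with no follow-up provided for

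*Combined protocol and SAP*

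**What the plan says.** Section 16, 10.1 answers the form's question about withdrawing subjects from the research without their consent. It gives two grounds.

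- Diagnosis: "Subjects diagnosed with opioid use disorder (OUD) or substance use disorder (SUD) during the study will be withdrawn and referred for treatment". This can occur in either arm.
- Behaviour: "Subjects exhibiting inappropriate behavior online or with a peer specialist may also be withdrawn". This has two alternative triggers, is permissive rather than mandatory, and does not say who decides or by what standard.

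The peer specialist appears in Section 16, 4.1.1, under the experimental intervention only: "As part of the application, participants will also have the option to connect with a peer support specialist at the VA". Of the control app, the same section says: "This app includes a pain monitoring functioning only". No contact between control participants and a peer specialist is described.

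Section 10.2 deals with a subject's own decision to withdraw. Data gathered up to that point may be used, and nothing is collected afterwards. Whether this also governs removal under 10.1 is not stated.

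Section 9.2 plans response rates and the percentage of missing data at each time point, between-group trends to inform the full-scale trial, mediation by use of specific SUMMIT components, and a Complier Average Causal Effect analysis. It does not mention withdrawals by arm or reason, and it does not say that participants are analysed as randomised.

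**The concern.** The opportunity to meet the peer-specialist trigger is created by assignment to SUMMIT and by use of one of its components. A removal on this ground is therefore a post-randomisation loss related to treatment. In an open-label trial, whoever exercises the discretion can know the arm.

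Three uses of the data are exposed. Retention and response rates are feasibility outputs, and a SUMMIT-specific loss could be read as ordinary dropout, because 9.1 carries a single overall allowance and 9.2 does not separate reasons. The between-group trends are meant to inform the full-scale design. And anyone removed under the peer trigger has, by definition, used the peer component, so the component-use mediation and complier analyses lose follow-up on people who bear directly on them. Trouble with the peer component is also something a feasibility trial should count, and no section says it will be.

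**Working it through.** **1. Which trigger can reach which arm.** The documents, set side by side:

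| Trigger | SUMMIT arm | Control arm |
|---|---|---|
| OUD/SUD diagnosis (10.1) | yes | yes |
| Behaviour with a peer specialist (10.1) | yes, optional contact within SUMMIT (4.1.1) | no contact described |
| Behaviour online (10.1, undefined) | yes | possible |

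The last cell rests on four places. Section 11, question 7.1 says of the two tools: "Both of these web-based applications will be used on their personal mobile phones". Section 16, 4.1.2 notes of the control app: "There is an option to sign up for an online account through the Manage My Pain app", although participants are advised against it. Section 16, 4.1.1 has surveys emailed to participants in general. It also states, after describing both arms: "In order to help participants set up their mobile applications, the study coordinator will set up a video appointment". No forum or chat exclusive to SUMMIT is described. So only the peer-specialist trigger is confined to one arm.

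**2. The plan's own figures.** Inputs from Section 16, 9.1: control rate 20%, difference 15 points, 80% power, two-sided alpha 0.05, one-sided 90% CI for the pilot, 25% dropout. Allocation is 1:1 (4.1.1).

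- Main trial, pooled-variance formula: n per arm = [1.960·√(2 × 0.275 × 0.725) + 0.842·√(0.20 × 0.80 + 0.35 × 0.65)]² / 0.15² = 137.9, rounded up to 138, giving 276 in total. This matches the plan.
- Pilot, taking an observed difference of zero and 20% in both arms: n per arm = 2 × 0.20 × 0.80 × (1.2816/0.15)² = 23.4, rounded up to 24, giving 48. This matches.
- Dropout: 48/(1 − 0.25) = 64. This matches.
- Per arm: 64/2 = 32 randomised, and 24 retained if dropout is 25% in each arm.

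The concern does not touch these calculations.

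**3. Cost of each removal.** The documents give no expected count, so k below is an assumption, and zero is possible. Each removal costs 1/32 = 3.1 points of SUMMIT retention. The table also shows the half-width of the one-sided 90% interval, 1.2816·√(0.16/(24 − k) + 0.16/24), assuming that common dropout has already used the full 25% allowance in both arms and that the k removals come on top.

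| k removed, SUMMIT only | Retained, SUMMIT vs control | Retention gap k/32 | Half-width |
|---|---|---|---|
| 0 | 24 vs 24 | 0 | 0.148 |
| 1 | 23 vs 24 | 3.1 points | 0.150 |
| 2 | 22 vs 24 | 6.25 points | 0.151 |
| 3 | 21 vs 24 | 9.4 points | 0.153 |

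The pilot size works with little to spare: two such removals take the half-width just past the 0.15 that it was chosen to stay under. The change is small, and it arises only if the dropout allowance is otherwise exhausted.

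**The case against.** The strongest reply is that the rule is narrow. It is permissive, peer contact is optional, and the number of cases may be nil. Diagnosis-based withdrawal and voluntary dropout apply to both arms. The study is described as not powered for between-group differences. In an open-label test of a package, attrition caused by a component is a property of the package. The sponsor also has a fair interest in keeping discretion over conduct towards a peer specialist.

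Most of this stands as a limit on size. A reader might infer that the whole behaviour rule can reach only SUMMIT participants; the undefined word *online* and the control arm's own online contacts rule that out. A reader might also infer that attrition is one-sided by design. It is not: one discretionary reason among several is unequally available.

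A reader might further compute an outcome bias. Three removed non-responders would turn a true 20% into (0.20 × 32)/29 = 6.4/29 = 22.1%. The documents do not support that figure. The count has no source, all three must be non-responders, and the calculation deletes them outright. Section 9.2 plans models with participants as random factors, which can use data collected before removal, and no section says that withdrawn participants are dropped from analysis.

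What the reply does not answer is the difference between a participant leaving because of a component and the protocol ending follow-up because of behaviour within it. The first is a finding about the package. The second is a loss that the trial imposes on itself and can avoid.

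**Conclusion.** The point holds in a limited form. One of the two involuntary withdrawal grounds falls unequally on the arms, because its peer-specialist trigger exists only where SUMMIT is assigned, while its online trigger is undefined and could reach either arm. Since removal is from the research and no follow-up is provided for, the rule can cause treatment-related loss among users of a SUMMIT component.

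Its size is 3.1 points of SUMMIT retention per case, on the basis of 32 per arm. The number of cases is unknown and may be zero. Neither the size nor the direction of any bias in the outcome rate can be derived from the documents. The conclusion assumes that control participants have no peer-specialist contact, as the arm descriptions imply, and that removal under 10.1 ends data collection. The second is the natural reading of withdrawal from the research but is not spelled out, because the statement about stopping collection sits in 10.2, under a subject's own decision.

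**What to change.** Amend the behaviour sentence in Section 16, 10.1 so that inappropriate behaviour with a peer specialist or online may end access to that feature but does not by itself end research follow-up. Define *online* in the same sentence.

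State that these participants stay in the remote survey, opioid-dose and adverse-event collection unless they withdraw or continued contact would be unsafe for staff. In 9.2, add that they are analysed as randomised and that each event is reported by arm and reason as a feasibility result.

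The cost is a few lines of text and continued, mostly remote, contact with a few difficult participants. The exception for staff safety keeps the discretion that the current wording was presumably meant to give. No sample size or schedule changes.
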